3.4 Secondary Endpoints

1. Clinical recovery and resolution of COVID-19 symptoms

1a. Sustained recovery and resolution rates of common COVID-19 symptoms:

(i.e., stuffy or runny nose, sore throat, cough, low energy or tiredness, muscle or body ache, headache, chills or shivering, feeling hot or feverish, nausea, vomiting, diarrhea, shortness of breath with exertion; impairment in sense of smell or taste)

Proportion of subjects in treatment group versus placebo group, respectively, who per symptom questionnaire on days 4, 7, 10, 14, 21, 28, 42, 60 post randomization have achieved for two consecutive days:

- o scores not higher than 0 for all symptoms
- o scores not higher than 1 for all symptoms
- o scores not higher than 0 for all symptoms other than impairment of taste or smell
- o scores not higher than 1 for all symptoms other than impairment of taste or smell
- *1b. Sustained improvement of global impression rates:* Proportion of subjects in treatment group versus placebo group, respectively, who per symptom questionnaire on days 4, 7, 10, 14, 21, 28, 42, 60 post randomization have answered for two consecutive days
 - "Yes" to "In the past 24 hours, have you returned to your usual health (before your COVID-19 illness)?"
 - "Yes" to "In the past 24 hours, have you returned to your usual activities (before your COVID-19 illness)?"
 - o "None" to "In the past 24 hours, what was the severity of your overall COVID-19 related symptoms at their worst?"
 - o "Mild" to "In the past 24 hours, what was the severity of your overall COVID-19 related symptoms at their worst?"
- 1c. Time to sustained recovery, resolution or improvement: comparison in treatment group versus placebo group, respectively of the number of days from randomization to the first day of achieving each item in 1a and 1b above.

2. Physical functions and parameters relevant to COVID-19

- **2a. Parameter rates:** Proportion of subjects in treatment group versus placebo group, respectively, who on days 4, 7, 10, 14, 21, 28, 42, 60 post randomization per thermometer or pulse oximeter reading experienced:
 - fever at any point between enrollment and day 2 post randomization and who were afebrile <38C
 - o oxygenation of SpO2>=96% or >93% in room air when resting
- 2b. Time to and length of parameters: comparison in treatment group versus placebo group, respectively of the number of days

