 - o from randomization to the first day of achieving sustained (i.e., at least 2 days) resolution of fever for subjects who presented with fever at any point between enrollment and day 2 post randomization

- with temperature <38C or >=38C experienced in total during the first 28 days post randomization
- o from randomization to the first day post randomization of achieving oxygenation of SpO2>=96% in room air when resting for subjects who presented with SpO2>93% and <96% in room air, when resting, at enrollment
- o with oxygenation of SpO2>= 96% or SpO2>93% in room air, when resting, in total during the first 28 days post randomization

3. COVID-19 related deterioration and mortality

- **3a. Deterioration and mortality rates:** Proportion of treatment group, versus placebo group, respectively, who per subject reporting or medical records by day 14, day 28 and by day 60 post randomization had experienced:
 - o an emergency department visit, other than at study enrollment or study visits
 - hospitalization for COVID-19
 - o hospitalization for COVID-19 requiring oxygen
 - hospitalization for COVID-19 requiring ICU
 - o hospitalization for COVID-19 requiring ventilation
 - o COVID-19 related death
 - death
 - hospitalization or death
- **3b.** *Time to and length of deterioration*: Comparison of treatment group versus placebo group, respectively, in the number of days
 - o from randomization until the first day of experiencing hospitalization for COVID-19
 - o of hospitalization for COVID-19 experienced in total by day 14, by day 28 and by day 60 post randomization
 - o of hospitalization for COVID-19 requiring oxygen experienced in total by day 14, by day 28 and by day 60 post randomization
 - of hospitalization for COVID-19 requiring ICU experienced in total by day 14, by day 28 and by day 60 post randomization
 - o of hospitalization for COVID-19 requiring ventilation experienced in total by day 14, by day 28 and by day 60 post randomization

4. WHO 9-Point Ordinal Scale

- 0. Uninfected or "no clinical or virological evidence of infection"
 - a. defined as subject answering "Yes" to "In the past 24 hours, have you returned to your usual health (before your COVID-19 illness)?"
- 1. Not hospitalized, no limitations on activities
 - a. defined as subject answering "Yes" to "In the past 24 hours, have you returned to your usual activities (before your COVID-19 illness)?"
- 2. Not hospitalized, limitation on activities

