5 STUDY DESIGN

5.1 Study Description

This is a phase 2 proof of concept randomized, double-blind, placebo-controlled trial with the purpose of assessing the safety, tolerability and treatment effect of the orally administered Caspase-1 inhibitor, belnacasan, for the treatment of patients with mild to moderate COVID-19. 20 subjects will be given 900 mg TID of belnacasan and 20 subjects will be given a placebo TID for 28 days, and assessments of safety, tolerability, and treatment effect will be performed for up to 60 days.

At the screening / baseline / day 1 Visit, subjects will provide informed consent and be screened for eligibility based on the Inclusion / Exclusion criteria identified in Section 5.3. Subjects will also receive the first dose of study drug at this visit once study eligibility has been confirmed, and the second dose of study drug will be taken approximately 8-12 hours after the first dose. Study drug will be continued three times daily (morning, mid-day, and nighttime doses) through day 28. Some patients identified will require a PCR-confirmed COVID test, having only had a rapid antigen test. Patients requiring a PCR test can either have one collected with screening labs prior to leaving the MedStar enrollment site or have these labs collected via a home-health research visit at no cost to the potential participant. Prior to study-specific procedures the study team will obtain their consent in-person or by remote consent process. An e-consent platform, Interlace, may also be used to document consent electronically. Once their COVID-19 status is confirmed via PCR they will complete the remainder of their screening/enrollment visit at either MedStar Washington Hospital Center or MedStar Franklin Square within the next 1 to 3 days. The remote consent

process and e-consent will follow MedStar institutional policies and procedures (MG.O-004.06 and MG.O-004.07).

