The trial duration will be approximately 60 days (8.5 weeks) for all subjects enrolled. As outlined in the Schedule of Events Table in Section 5.2, over the course of the study duration, all subjects will use a diary to record IP intake as well as symptoms and activity levels with guidance to do so at the same time each day; assess physical parameters using a study-provided thermometer and pulse oximeter for which detailed instructions will be provided at enrollment; be assessed at regular intervals by the Study Team via telephone calls and in-person follow-up clinic visits; and give blood for laboratory tests.

An experienced and appropriately licensed Study Team member will conduct the telephone study visits and be the point of contact if subjects experience deterioration, such as high temperatures (above 38C) or low oxygen saturation levels (below 93%). The primary coordinator of the trial will be a registered nurse, experienced in vital sign and symptom review, with the ability to escalate any medical concerns to the Principal Investigator as it relates to worsening of the subjects' illness or adverse event identification. The Principal Investigator or delegated Sub-Investigator, as documented on the study delegation log, is well-versed in delegation of appropriate tasks as defined by licensure and scope of practice and will work closely with the study team to assure delegation remains appropriate through the duration of the trial. Medical advice or direction will only be given by sufficiently licensed study personnel, either mid-level providers or physicians, in partnership with their primary care team.

Subjects will be instructed to fill in symptoms assessment, overall health assessment, temperature and oxygen saturation levels in the diary each morning; and to note in the diary 3 times per day that they have taken the study drug. The Study Team will conduct in-person visits with the subjects on days 7, 14, 21, and 28 and telephonic visits with subjects on days 1, 4, 10, 42, and 60; as well as when / if subjects contact them due to symptom deterioration as instructed. Subjects will receive reminders to complete the diary via text message and / or email. Subjects who prematurely discontinue study drug for any reason will be asked to have an Early Termination (ET) visit the day the last study drug dose is administered; moreover, they will be encouraged to stay enrolled so that further safety and outcome information can be collected and analyzed.

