5.2 Study Assessments

Table 1: Schedule of Events: **1** = In-Person; **2** = Telephone; **3** = Subject Self-Tracking

Time Point (Days)	Screen / enroll	D19	D4	D7	D10	D14	D21	D28	D42	D60	ET ¹⁰
STUDY TEAM											
Inclusion / Exclusion	İ										
Consent	İ							\			
Screening Tests ^{1, 12}	İ					1					
Demographics	İ										
CXR or CT ¹³	İ										
Physical Exam	İ			İ		1	Ť	Ţ			ţ
Vitals ²	İ			İ		İ	İ	İ			İ
EKG	İ			İ		İ	İ	İ			İ
CoV-2 N/P ³	İ					İ		Ť			Ť
Standard labs ^{4, 12}	İ			İ		Ì		Ť			Ť
Blood draws ^{5, 12}	İ			İ		1	Ť	Ť			İ
Immunology tests ^{6, 12}	İ			İ		Ì	Ť	Ť			Ť
CoV-2 blood ^{7, 12}								Ť			Ť
AE assessment	İ	2	2	İ	2	Ţ	İ	Ī	2	~	Ĭ
Symptoms assessment	İ	2	2	İ	2	Ţ	İ	İ	2	~	İ
WHO 9-Point Scale ⁸	İ	2	2	İ	2	Ţ	İ	İ	2	2	İ

SUBJECTS (as recorded in study diary)						
IP/placebo intake	Three times per day through day 28 or ET					
Temperature ¹¹	Daily via thermometer through day 28 or ET; subject will report via telephone to					
	study team at Day 42 & 60					
SpO2 resting ¹¹	Daily via pulse oximeter through day 28 or ET; subject will report via telephone to					
	study team at Day 42 & 60					
Symptom tracking	legistrian One time per day through day 28 or ET; subject will report via telephone to study					
	team at Day 42 & 60					

¹Screening tests: HIV, Hepatitis B, Hepatitis C, and pregnancy (serum pregnancy test for women of child-bearing potential per MedStar definition at enrollment and at day 14).

²Vital signs: oral temperature, heart rate, systolic blood pressure.

³Quantitative nasopharyngeal SARS-CoV-2 RNA testing (RT-PCR): nasopharyngeal or throat swabs will be used; any FDA-approved or commercial testing method will be acceptable. A home health agency may be used to confirm COVID-19 by RT-PCR in the subjects' home in the event their initial testing did not include PCR, to ensure expeditious resulting and appropriate inclusion into the trial. If home health is used to collect the PCR test or there is a delay in PCR resulting at initial screening, the subject will return to either MedStar Washington Hospital Center or MedStar Franklin Square for completion of the screening/enrollment visit in 1 to 3 days, once positive PCR is confirmed, to complete all study procedures including randomization and medication dosing under observation. ⁴Standard labs: serum chemistry, coagulation tests and hematology. Pregnancy tests for women of childbearing potential at screening, day 14 and end of treatment.

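### Two secondary endpoint definitions are wrong as written: the Mild item in 1b and 1c does not count full recovery, and one pair of diary answers meets both level 0 and level 2 of the ordinal scale

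*Combined protocol and SAP*

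**What the plan says.** **Symptom severity.** Section 3.4, item 1b, is headed as sustained improvement and lists None and Mild as separate answers to the overall-severity question, each required on two consecutive days. The Mild item reads "Mild' to 'In the past 24 hours, what was the severity of your overall COVID-19 related symptoms at their worst". Item 1c then measures time to each 1a and 1b item separately. Item 1a uses a cumulative form instead: "scores not higher than 1 for all symptoms".

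**Ordinal scale.** For non-hospitalized subjects, section 3.4, item 4, defines level 0 as Yes to the usual-health question, level 1 as Yes to the usual-activities question, and level 2 as No to the usual-activities question. The diary (section 12.2) asks the two questions separately. Table 1, footnote 8, only refers back to the endpoint list. Level 6 is intubation, and level 7 includes invasive mechanical ventilation.

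**Fever.** Item 2a counts subjects with "fever at any point between enrollment and day 2 post randomization and who were afebrile <38C", and 2b times "resolution of fever for subjects who presented with fever at any point between enrollment and day 2 post randomization". The SpO2 item in 2b fixes its group at baseline: "for subjects who presented with SpO2>93% and <96% in room air, when resting, at enrollment".

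The Synopsis repeats all of these definitions.

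**The concern.** The secondary objective (section 3.3) is to estimate effect sizes, and section 8.7 says the estimate will inform a larger trial. An item labelled improvement should not score a fully recovered subject as a failure. If the drug moves subjects through Mild to None faster, the Mild item can favour placebo because the drug works.

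A scale on which the same two answers fit two levels leaves the analyst a coding choice. For a subject who starts at level 2, those answers are either a two-point improvement or no change. If the choice is made after the data are seen, the results of 4a to 4c depend on it.

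**Working it through.** The plan gives no recovery rate and no figure for these items, so there is nothing of its own to reproduce. All rates below are assumptions.

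**1. The Mild item.** Assume daily states Moderate, Mild and None, all subjects Moderate on day 1, no relapse, and the same daily probability *a* for Moderate to Mild and for Mild to None. Then:

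- Mild on day d and the day before: (d-2) × a × (1-a)^(d-2)
- None or Mild on both days: 1 - (1-a)^(d-2)
- Two consecutive Mild days at any time by day d: [1 - (1-a)^(d-2)] × (1-a)

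Example, day 10, placebo a = 0.20, drug a = 0.40:

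- Mild: placebo 8 × 0.20 × 0.80^8 = 26.8%; drug 8 × 0.40 × 0.60^8 = 5.4%; difference -21.5 points (before rounding).
- None or Mild: placebo 1 - 0.80^8 = 83.2%; drug 1 - 0.60^8 = 98.3%; difference +15.1 points.

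Drug minus placebo, in points, where the drug speeds both steps:

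| Daily rate, placebo / drug | Mild, day 10 | None or Mild, day 10 | Mild, day 14 | None or Mild, day 14 | Ever Mild by day 10 | Ever Mild by day 14 | Ever Mild by day 28 |
|---|---|---|---|---|---|---|---|
| 0.20 / 0.25 | -6.8 | +6.8 | -7.0 | +3.7 | +0.9 | -1.9 | -4.8 |
| 0.20 / 0.30 | -13.0 | +11.0 | -11.5 | +5.5 | -0.6 | -5.5 | -9.8 |
| 0.20 / 0.40 | -21.5 | +15.1 | -15.4 | +6.7 | -7.6 | -14.6 | -19.8 |
| 0.12 / 0.18 | -5.1 | +15.5 | -11.1 | +12.3 | +8.9 | +5.4 | -3.3 |
| 0.12 / 0.24 | -13.2 | +24.8 | -20.4 | +17.9 | +11.2 | +4.2 | -8.9 |

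On day 4 the Mild item still favours the drug in all five scenarios (+2.5 to +9.1). By day 7 it is negative in four of five (-17.2 to +1.7).

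For 1c, Cox hazard ratios were simulated with 40,000 subjects per arm. In table order, Mild gives 0.98, 0.93, 0.77, 1.10 and 1.06; None or Mild gives 1.31, 1.61, 2.30, 1.56 and 2.17. The effect is always weakened but clearly reversed only in the third scenario.

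**2. Scale levels met by each pair of answers.**

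| Usual health | Usual activities | Levels met |
|---|---|---|
| Yes | Yes | 0 and 1 |
| Yes | No | 0 and 2 |
| No | Yes | 1 |
| No | No | 2 |

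Item 4a treats 1 to 0 as an improvement and 1 to 1 as sustained. If level 1 outranked level 0 for Yes/Yes, level 0 could be reached only by losing usual activities. So 4a implies that level 0 takes precedence there. It says nothing about Yes/No.

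*Size in 4a.* For the item on moving from level 2 to level 1 or 0, one Yes/No subject is 1/20 = 5 points if all 20 start at level 2, and 1/10 = 10 points if only 10 do and they form the denominator.

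*Size in 4b.* The choice of rule shifts the mean difference by 2 × (Yes/No share on drug minus share on placebo). Assume shares in the table's row order of 50/5/20/25% on placebo and 65/10/10/15% on drug.

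- Yes/No scored 0: placebo 0.20 + 2 × 0.25 = 0.70; drug 0.10 + 2 × 0.15 = 0.40; difference -0.30.
- Yes/No scored 2: placebo 0.70 + 2 × 0.05 = 0.80; drug 0.40 + 2 × 0.10 = 0.60; difference -0.20.

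The shift is 2 × (0.10 - 0.05) = 0.10. With equal shares it is zero.

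**The case against.** **The plan limits the harm.** These are secondary endpoints in a hypothesis-generating trial. None is reported as its own item, and 1a already has cumulative items. This stands, and it caps the importance of the point. It does not repair the Mild item, which would still be reported with its own effect estimate.

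**The size depends on the model.** This also stands. If the drug acts only on Mild to None, the Mild item is negative at day 10 (-11.4 to -17.8 points in three scenarios), but None or Mild shows exactly zero, so the replacement also misses that effect and only the None item shows it. Those scenarios are therefore left out of the main result. If the drug acts only on Moderate to Mild, the Mild difference is just -0.4 at day 10 and -3.3 at day 14. By day 28 the visit-day differences are under 2 points in six of the nine scenarios. With 20 per arm, chance dominates: with daily rates of 0.20 and 0.30, 95% of estimated 1c hazard ratios would fall between about 0.47 and 1.90. A reader might infer that the item always reverses the effect. It does not.

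**The precedence implied by 4a could be extended to score Yes/No as 0.** It could, but the plan does not say so. That rule would also put a subject who reports not being back to usual activities in the uninfected category, against the meaning of level 2.

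**The fever window.** A reader might infer that the 2a/2b fever definition is a third error, since "Subjects will also receive the first dose of study drug at this visit once study eligibility has been confirmed" and so membership can depend on treatment. The documents do not support calling it wrong. It is computable and internally consistent. Because "Subjects will be instructed to fill in symptoms assessment, overall health assessment, temperature and oxygen saturation levels in the diary each morning", the window adds only one or two post-dose home readings, and 2b also counts days below and at or above 38C without restriction. It carries a risk of bias, but with no fever rate given, the size cannot be stated. A baseline-only group has its own weakness: antipyretics are not withheld (section 5.1), so one reading can miss fever.

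**Conclusion.** Two definitions need correcting.

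- **Mild item.** That a fully recovered subject fails it follows from the wording alone. Its size rests on assumed recovery rates, all subjects starting Moderate, and no relapse. When the drug speeds both steps and the item is read at the visit, the Mild item gives -5.1 to -21.5 points at day 10 and -7.0 to -20.4 at day 14. None or Mild gives +6.8 to +24.8 and +3.7 to +17.9. If the item means ever achieved by that day, reversal comes later: two of the five scenarios at day 10, three at day 14 and all five at day 28.
- **Scale.** The Yes/No overlap is a matter of text, with no assumption needed. It affects 4a to 4c, but not the items on reaching level 4 or 6. The smaller overlap between levels 6 and 7 affects 4b (averages and worst value) and the day counts in 4d.

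The changes should be made, but nothing here touches the primary safety endpoint or the safety decision rule. The fever window is a matter for an optional sensitivity analysis.

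**What to change.** Make these edits in section 3.4 and the Synopsis before unblinding.

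1. **1b and 1c.** Replace Mild with None or Mild. For both, include only subjects not already None or Mild at a pre-dose answer to the overall-severity question, since a subject who starts at Mild and stays there has not improved. Record that answer at the enrollment symptoms assessment; Table 1 schedules the assessment but does not say it includes this question.
2. **Scale levels 0 to 2.** Make them mutually exclusive, with one stated rule for Yes/No. One option that keeps level 2 true to its label is: 0 = Yes to both questions; 1 = activities Yes and health No; 2 = activities No.
3. **Levels 6 and 7.** State which takes precedence.
4. **Optional, fever.** Add a sensitivity analysis of 2a/2b in subjects with temperature at or above 38C before the first dose. If 10% to 40% are febrile then (assumed), that is 40 × 0.10 = 4 to 40 × 0.40 = 16 subjects, so it would be descriptive.

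The cost is wording plus one confirmed question at enrollment; everything else uses data already scheduled. The restriction in edit 1 may shrink the 1b and 1c denominators, which should be reported. These edits do not make the two-consecutive-day items computable at days 42 and 60: symptoms are tracked "One time per day through day 28 or ET; subject will report via telephone to study" team, and those two days are single phone reports.

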For this trial we will treat for a maximum of 28 days. Our rationale for this timeframe is that while there is an expectation that the illness lasts up to 12-15 days in those who recover without complication, others will endure a longer duration, and some will experience persistent, new onset or worsening disease related symptoms. A recent study from the Centers for Disease Control and Prevention (https://www.cdc.gov/mmwr/volumes/70/wr/mm7017e3.htm?s cid=mm7017e3 w) found that among 3,171 non-hospitalized adult COVID-19 patients, 69% had one or more outpatient visits 28–180 days after the diagnosis. Two thirds had a visit for a new primary diagnosis, and approximately one third had a new specialist visit. Symptoms potentially related to COVID-19 were common new visit diagnoses. Visits for these symptoms decreased after 60 days but for some patients continued through 120–180 day. Furthermore, some individuals develop sequela that are likely related to post-viral immune dysregulation in the first few months albeit there is little known about this group. Though we are unlikely to learn about the effect of the drug in this latter population we do need to establish safety for a duration that includes the other groups mentioned above.

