Heart: troponin; Kidney: creatinine, blood urea nitrogen (BUN), electrolytes (calcium, carbon dioxide, chloride, potassium, sodium, magnesium); Pancreas: glucose, HbA1c, lipase; Liver: ALT, AST, ALP, total bilirubin; Muscle weakness: creatinine kinase; Hematology: red blood cell count, hemoglobin, platelet count, prothrombin time (PT), partial thromboplastin time (PTT), ddimer; Immunology: white blood cell count, neutrophils, lymphocytes, monocytes, eosinophils, T cells, SARS-CoV-2 viral load in nasopharyngeal sample, SARS-CoV-2 serology in blood; Inflammation: CRP, ferritin, LDH, caspase-1, IL-18, IL-1β, IL-1 receptor antagonist, gasdermin D, IL-6, TNF-α, G-CSF

- *5a) Analysis and comparison of* surrogate markers of COVID-19 related inflammation and organ involvement as determined by biochemistry, hematology, and immunology labs and studies, in treatment group versus placebo group, respectively, for
 - o values on days 1 (enrollment), 7, 14, 21, 28 post randomization
 - o changes from enrollment to days 7, 14, 21, or 28 post randomization
 - o changes between days 7, 14, 21, 28 post randomization
- *5b) Reference range rates:* proportion of treatment group versus placebo group, respectively, who experience normal / in-range values for a given marker at days 7, 14, 21, 28 post randomization

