5.3 Selection Criteria

Inclusion Criteria:

- Subject (or legally authorized representative) provides written informed consent prior to the initiation of any study procedures.
- Subject understands and agrees to comply with planned study procedures, including using the diary.
- Subject agrees to the collection of nasopharyngeal swabs and venous blood per protocol.
- Subject is male or non-pregnant female adult ≥18 years of age at time of consent.
 - Women with a history of menstruation must agree to use two methods of contraception, at least one of which is highly effective, for the duration of the study as well as to undergo additional pregnancy testing during the study.
- Subject has a laboratory confirmed SARS-CoV-2 infection as determined by RT-PCR assay prior to enrollment.
- Subject has evidence of either mild or moderate COVID-19 illness of less than 7 days from first onset, with minimal baseline symptom severity based on patient-reported FDA scoring system defined as follows:
 - Subject presents with at least two common symptoms of COVID-19 from the following list: stuffy or runny nose, sore throat, cough, low energy or tiredness, muscle or body ache,

⁶Immunology tests: COVID-19 relevant immunology labs (see Appendix 12.1 for complete list). See footnote to Appendix 12.1 as certain labs will be sent to and resulted from outside lab facilities.

⁷Quantitative blood SARS-CoV-2 antibody testing: Blood samples will be used; any FDA-approved or commercial testing method will be acceptable.

⁸WHO 9-point scale: see description of secondary end points for details.

headache, chills or shivering, feeling hot or feverish, nausea, vomiting, diarrhea, shortness of breath with exertion (without supplemental oxygen requirement) with a score of 2 or higher; impairment in sense of smell or taste with a score of 1 or higher **OR**

- Subject presents with any (i.e., at least one) symptom of COVID-19 as defined above AND clinical evidence of moderate COVID-19 as defined by FDA guidance for industry (such as respiratory rate >20 breaths per minute, heart rate >90 beats per minute, with oxygen saturation >93% on room air at sea level).
- Subject presents with high-risk for COVID-19-related inflammation determined by at least one comorbidity, including obesity, diabetes, hypertension, stable heart disease, respiratory disease, and / or non-severe fatty liver disease.

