8.2 Analysis Methods

General Methods

FDA Data Standard Guidelines will be followed. Continuous variables will be summarized using the number of observations, number of observations above the limit of quantification (if applicable), mean, standard deviation (SD) median, and range. Categorical variables will be summarized using frequency counts and percentages. Comparison of belnacasan (VX-765/RVT-201/MSR-001) and placebo groups will utilize Poisson regression for counts, Cox proportional hazards regression for time-to-event data and mixed effects models for continuous and categorical data obtained over study days.

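### Viral load has no day 7 or day 21 swab although endpoints 5a and 5b analyse those days, and the first scheduled on-treatment value comes about two to three weeks after symptom onset

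*Combined protocol and SAP*

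**What the plan says.** Section 3.4 lists "SARS-CoV-2 viral load in nasopharyngeal sample" among the endpoint 5 markers. Endpoint 5a then applies one list of days to every marker: "values on days 1 (enrollment), 7, 14, 21, 28 post randomization", "changes from enrollment to days 7, 14, 21, or 28 post randomization", and changes between days 7, 14, 21 and 28. Endpoint 5b compares the proportion in range on days 7, 14, 21 and 28. Nothing exempts viral load from these days.

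In Table 1 (section 5.2), the swab row is marked at screening/enrollment, day 14, day 28 and early termination. The day 7 and day 21 cells are blank, although both are in-person visits. Footnote 3 calls the test quantitative, but says "nasopharyngeal or throat swabs will be used; any FDA-approved or commercial testing method will be acceptable". No detection or quantification limit is stated.

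On timing, section 5.3 requires "mild or moderate COVID-19 illness of less than 7 days from first onset". If the PCR result is pending, footnote 3 has the subject return "for completion of the screening/enrollment visit in 1 to 3 days, once positive PCR is confirmed". The only natural-history figure is in section 1.3, where the expectation is that "the illness lasts up to 12-15 days in those who recover without complication".

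On analysis, section 8.2 will report how many values lie above the limit of quantification. Section 8.5 sends change in continuous endpoints to mixed models and proportions to chi-square or mixed logistic models. Neither 8.5 nor 8.6 says how values below the limit enter the comparison.

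**The concern.** Two of the days on which viral load is to be analysed have no specimen. The missing day 7 matters more than day 21: it is the earliest in-person visit on treatment, and a difference in clearance may be best seen while most subjects still have measurable virus. Inflammation markers are drawn that day, so the trial would have early cytokine data without matching virus data.

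The second issue is what later values can carry. Once a subject is below the assay limit, the laboratory returns a floor, not a quantity. If floors enter a mixed model for change as if they were measurements, the change is capped at baseline minus the floor, and a true difference in speed of clearance is compressed. What is at stake is the effect-size estimate for one marker, in a trial whose stated purpose is to estimate effect sizes for a larger one.

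**Working it through.** **1. Schedule against endpoints.** The physical exam row of Table 1 resolves to screening, days 7, 14, 21, 28 and early termination, exactly the in-person visits, so the column positions can be trusted. For the swab row:

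| Analysis | Days or pairs named | Supported by a scheduled swab |
|---|---|---|
| 5a values | 1, 7, 14, 21, 28 | 3 of 5 (1, 14, 28) |
| 5a change from enrollment | to 7, 14, 21, 28 | 2 of 4 (14, 28) |
| 5a change between days | 6 pairs from 4 days | 1 of 6 (14 to 28) |
| 5b in range | 7, 14, 21, 28 | 2 of 4 (14, 28) |

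The early-termination swab is tied to stopping the drug, not to a fixed day, so it does not fill the gap.

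**2. Time since onset.** Onset is 0 to just under 7 days before screening, a pending PCR can add up to 3 days, and day 1 is the first dose. Day 14 therefore falls between 0 + 13 = 13 and about 7 + 3 + 13 = 23 days after onset. Day 28 falls between 27 and about 37, and a day 7 swab would fall between 6 and about 16. Against 12 to 15 days of uncomplicated illness, day 14 is mostly around or after recovery. That figure is illness duration, not viral shedding, so it makes low values plausible without proving them undetectable.

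**3. Share below detection.** The documents give no viral-load mean, SD, decline rate or limit. Assumptions: enrollment mean μ of 6 to 7 log10 (SD 1.5), decline d of 0.25 to 0.45 log10/day (SD between subjects 0.1), assay noise SD 0.5, limit L of 2 to 3 log10. Then

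P(below) = Φ[(L − (μ − d·t)) / √(1.5² + 0.5² + (0.1·t)²)].

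| Day | SD | Most favourable (μ 7, d 0.25, L 2) | Least favourable (μ 6, d 0.45, L 3) |
|---|---|---|---|
| 7 | √2.99 = 1.73 | mean 5.25, z = −1.88, 3% | mean 2.85, z = 0.09, 53% |
| 14 | √4.46 = 2.11 | mean 3.50, z = −0.71, 24% | mean −0.30, z = 1.56, 94% |
| 28 | √10.34 = 3.22 | mean 0.00, z = 0.62, 73% | mean −6.60, z = 2.99, nearly 100% |

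**4. What the floor does, for an average subject** (start 6.5, limit 2.5, decline 0.35/day).
- *Day 7:* 6.5 − 2.45 = 4.05 on placebo. With 40% faster decline (0.49/day), 6.5 − 3.43 = 3.07. Both are measurable, and the difference is 0.98.
- *Day 14, faster:* true values are 1.60 and −0.36. Both are reported as 2.5, so a true difference of 1.96 shows as 0.
- *Day 14, 40% slower* (0.21/day): 6.5 − 2.94 = 3.56 against the floor of 2.5, so 1.06 remains visible.

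The floor hides acceleration far more than delay.

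**5. Power.** Simulation with 20 per arm, start 6.5, limit 2.5, the SDs above, floored values, baseline-adjusted ANCOVA, two-sided 5%, decline 0.25 to 0.45/day:

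| Effect | Day 7 | Day 14 | Day 28 |
|---|---|---|---|
| 40% faster decline | about 52-78% | about 12-53% | about 0-14% |
| 40% slower decline | not needed for the point | about 68-86% | some power only if decline is slow |

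For faster decline, days 7 and 14 tie at 0.25/day (both a little over 50%). Day 7 leads clearly at 0.35/day (over 70% against 47%) and at 0.45/day (close to 80% against about 12%). The percentages shift with modelling details; the near-tie at slow decline and the day 7 lead at faster decline are the results to rely on.

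The plan has no viral-load figure to reproduce. The detectable difference of over 60% in section 8.7 concerns rate ratios and does not bear on this marker.

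**The case against.** A reader might infer that this endpoint can hardly show any drug effect, or that a null result would say nothing about clearance. The documents do not support that. They hold no viral-load data, and even under the assumptions above the share below detection at day 14 runs from 24% to 94%, so a majority is not established. Day 14 ties with day 7 at the slowest decline and retains about 68-86% power for a 40% slower decline, even with naive flooring. Delayed clearance is a relevant question for an anti-inflammatory drug. Only the day 28 share is high across the whole range.

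Other objections also have weight. The 5a day list is generic, and the same mismatch affects other markers: standard labs have no day 21 draw, and serology is drawn only at day 28 and early termination. Endpoint 5b, with the chi-square and logistic models in 8.5, already comes close to a comparison of proportions undetectable, although in range is not defined for viral load. The markers closest to the mechanism are drawn at every in-person visit. The trial calls itself hypothesis-generating and probably underpowered, and its primary endpoint is safety.

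These points limit the consequence but do not remove the defect. Analyses are named for days without a specimen, and a value never collected cannot contribute to an effect-size estimate.

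**Conclusion.** The mismatch is certain and rests on the documents alone: for viral load, the day 7 and day 21 analyses in 5a and 5b cannot be done. It is also documented that the first scheduled on-treatment swab falls about 13 to 23 days after onset and that no method is given for values below the limit.

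The loss of information from omitting day 7 is conditional on assumed kinetics. For faster clearance it ranges from none, at the slowest decline, to a fall from close to 80% to about 12% power at the fastest. Day 14 remains useful, especially for delayed clearance. Day 28 has 73-100% of values below detection and little power for acceleration.

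This concerns one secondary marker and does not touch the primary safety endpoint. It should be corrected because the correction is cheap and the early value cannot be recovered later.

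**What to change.** - **Table 1:** add the nasopharyngeal swab at the existing day 7 in-person visit and keep days 14 and 28. Cost: 40 subjects × 1 = about 40 more swabs with their assays, no new visit, no change to blood volumes, and a protocol amendment. Moving the day 28 swab to day 7 would avoid extra swabs, but it would lose late persistence and break 5a and 5b at day 28, so adding is preferable.
- **Section 3.4, 5a and 5b:** restrict the days for viral load to enrollment and days 7, 14 and 28, dropping day 21. Use the same edit to align the other markers with Table 1, one by one.
- **Section 8.5:** state the assay limit, which requires settling the specimen type and assay that footnote 3 leaves open. Analyse log10 viral load adjusted for baseline, with values below the limit treated as left-censored (a Tobit model or its repeated-measures form).
- **Section 8.5 and 5b:** report the proportion undetectable at days 14 and 28, and define undetectable as in range for this marker.
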